9. DATA MANAGEMENT

9.1. Definition of source data

All evaluations that are reported in the eCRF must be supported by appropriately signed identified source documentation related to but not limited to:

- Subject identification, last participation to a clinical trial, medical history, previous and concomitant medication;
- Physical examination, blood pressure and heart rate, body weight, BMI, subject habits;
- Dates and times of study drug administration;
- Pharmacokinetic time points;
- Laboratory assessments, meals;
- AEs.

9.2. Source document requirements

According to the guidelines on GCP, the Monitoring Team must check the eCRF entries against the source documents, except for the pre-identified source, data directly recorded in the Case Report Form. The Informed Consent Form will include a statement by which the subject allows the Sponsor's duly authorized personnel and the regulatory authorities to have direct access to source data which supports the data on the Case Report Forms (e.g. subject's medical file, appointment books, original laboratory records, etc.). These personnel, bound by professional secrecy, will not disclose any personal identity or personal medical information.

9.3. Use and completion of Case Report Forms (CRFs) and additional request

9.3.1. Data collection

All clinical data will be reported electronically by the Investigator or authorised designee on a web-based electronic Case Report Form (eCRF). This eCRF is specifically designed for the study and developed by the Data Management Department of Eurofins Optimed using LifeSphere EDC® 5.2, a validated Electronic Records/Electronic Signature-compliant (21 CFR Part 11) application of Aris Global.

Should a correction be made, the corrected information will be entered in the eCRF and the initial information will be tracked in the audit trail.

ECG Central reading data will be transferred in the study database prior to database freeze.

9.3.2. Responsibilities

The Investigator or authorised designee is responsible for the timeliness, completeness, consistency and accuracy of all observations and other data pertinent to the clinical investigation in the eCRFs and PV forms.

The Investigator will ensure that all data are entered promptly (within 2 days) after the evaluation has occurred, in accordance with source documents and specific instructions accompanying the eCRFs, designed specifically for the study.

The Data Management Department of Eurofins Optimed will provide all tools, instructions, and training necessary to complete the eCRF, and each user will be issued a unique username and password.

The data management of Eurofins Optimed will be responsible for data processing, in accordance with the CRO data management procedures.

9.3.3. Data Management

During the study, through regular data collection and monitoring, clinical data reported in the eCRFs will be integrated into the clinical database. Computerised logic and/or consistency checks will be

Temp-UPC-853-C du 07/08/2017

systematically applied in order to detect errors or omissions. Queries will be generated and submitted through the electronic data capture (EDC) system to the investigator sites for resolution (queries should be answered within 7 days).

Correction will be made either automatically from the immediate completion or following the review of the data during the Eurofins Optimed monitoring. An audit trail, which will be initiated at the time of the first data entry, allows tracking all modifications.

The Data Management Department of Eurofins Optimed may generate additional requests to which the Investigator must respond electronically by confirming or modifying the data questioned. The requests with their responses will be implemented to the eCRFs.

Each step of this process will be monitored through the implementation of individual passwords and regular backups to maintain appropriate database access and to ensure database integrity.

When eCRFs are complete and all queries have been answered, the Investigator has to sign the eCRFs. Then eCRFs are locked and no modification is possible anymore.

After integration of all corrections in the complete set of data, the database will be locked and saved before being released for statistical analysis.

After database lock, a Patient Data Report (PDR) that consists of the printing out an entire casebook for a subject will be generated for each subject in .pdf format. A CD-ROM of PDRs will be kept at site and another one will be sent to the sponsor for archiving.

10. STUDY MONITORING

EUROFINS OPTIMED will perform the study in accordance with this protocol, GCP and the applicable regulatory requirements and the contract with the Sponsor.

The Investigator is required to ensure compliance with the Investigational Product schedule, visit schedule and procedures required by the protocol. The Investigator agrees to provide all information requested in the Case Report Form in an accurate and legible manner according to the instructions provided and to ensure direct access to source documents to Sponsor representatives.

The Sponsor is responsible to Health Authorities for taking all reasonable steps to ensure the proper conduct of the study as regards ethics, protocol compliance, integrity and validity of the data recorded on the Case Report Forms. Thus, the main duty of the Monitoring Team is to help the Investigator and the Sponsor maintain a high level of ethical, scientific, technical and regulatory quality in all aspects of the study. Monitoring activities have been delegated by the Sponsor to Eurofins-Optimed which will appoint 2 monitors (one blinded monitor and one unblinded monitor who will specifically proceed to monitoring activities at pharmacy level). Co-monitoring visits with the Sponsor representative are possible only on blinded data.

Should repeated breaches to the protocol, the GCP or the current regulation in force occur, which the Investigator would not take in account for improvement, then the Monitor would inform the Sponsor of these breaches. The Sponsor will notify these deliberate and repeated breaches to National Health Authorities.

11. STATISTICS

11.1. Description of the statistical methods

The statistical analysis will consist of individual data listings and descriptive statistics performed by EUROFINS OPTIMED (baseline characteristics, safety and study conduct), using the SAS[®] computer program (release 9.4).

The pharmacokinetic and pharmacodynamic data will be analysed by PhinC Development.

All individual data for all included subjects will be presented in data listings, sorted by subject within dose group.

Demographic and baseline characteristics data will be summarized by dose group and overall. On-product/treatment data will be summarized by dose group and overall.

For safety parameters with evaluation before dosing and in case of rechecked value(s) for one subject, only the last observation will be used in descriptive statistics and derivations of other parameter values. After dosing, only observations planned in the protocol will be used in descriptive statistics.

11.1.1. Descriptive statistics

Descriptive statistics for quantitative parameters will be provided using mean, Standard Deviation (SD), Standard Error of the Mean (SEM), minimum, median, maximum, and number of observations, and descriptive statistics for qualitative parameters will be provided using frequencies (n) and percent frequencies (%).

11.1.1.1. Subject demographic characteristics, medical history and diagnoses

Continuous variables (age, height, weight, BMI and qualitative variables will be summarized in descriptive statistics for all distinct study populations.

Results of laboratory screen (drug abuse), serology and alcohol breath test will be summarized by visit. Medical history will be listed and summarized by system organ class and preferred term, (Medical Dictionary for Regulatory Activity (MedDRA)). Abnormal physical findings at baseline will be listed.

11.1.1.2. Previous medications

Previous medications will be coded according to the World Health Organization-Drug Dictionary (WHO-DD). Subjects who took medications that were stopped before the first study drug dosing will be listed.

11.1.1.3. Baseline safety parameters

Individual safety data (clinical laboratory, vital signs, ECG, questionnaires) measured before the first drug administration will be checked for validity of entrance criteria, and abnormalities will be documented. Individual abnormalities before dosing will be flagged in data listings (and presented along with post-dose measurements in the statistical appendices).

11.1.1.4. Study drug and concomitant therapy

Drug dispensing information and details of drug dosing (actual products/treatment received, actual dose received, date and time of drug intake) for each subject will be listed by dose group.

Concomitant treatments will be coded according to the World Health Organization-Drug Dictionary (WHO-DD; most recent version at the time of study start). Subjects who received concomitant treatments along with the study drug will be listed by dose group and subject. If relevant, concomitant medications will also be summarized by anatomic class and therapeutic class for each treatment group and overall subjects, presenting the frequency of subjects (n) taking a given medication and the number of occurrences of each medication.

11.1.2. Analysis of principal criteria

11.1.2.1. Adverse event

AEs will be coded according to the most recent version at the time of study start of the Medical Dictionary for Regulatory Activity (MedDRA). They will be classified into pre-defined standard categories according to chronological criteria:

- Treatment emergent AEs (TEAE): AEs that occurs for the first time or if present before worsened during an exposure to drug(s).

- Non-treatment emergent AEs (NTEAE): AEs that occurs before the study drug administration (also called "pre-dose event").

An AE occurring during the follow-up will be related to the last day of treatment administration received. AEs will be individually listed per subject number, presenting: assigned dose group, verbatim, MedDRA Primary System Organ Class, MedDRA Preferred Term, treatment-emergence (TEAEs or not=NTEAEs) date and time of onset, date and time of last study drug administration before AE, duration, time from onset since last study drug administration, frequency, severity and seriousness, relationship to study drug (with justification is assessed related), the required action taken (e.g. corrective treatment, hospitalisation) outcome and if it is a reason for drop-out.

The non-treatment emergent AEs will be summarised by System Organ Class and Preferred Term for the safety set.

The treatment emergent AEs will be summarised by Primary System Organ Class, Preferred Term and dose group for the safety set. It will consist in the evaluation of the number of AEs and the number of subjects reporting these AEs.

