2. STUDY OBJECTIVES AND PURPOSE

2.1. Primary objective

To assess the safety and tolerability of DNDI-6148 after single oral doses administered as oral suspension of DNDI-6148 in healthy male subjects, compared to matching placebo.

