3.4. Expected duration of subject participation

3.4.1. Description and duration of trial periods

For the cohorts 10 mg, 20 mg, 40 mg and 80 mg:

- Screening within 28 days prior to the first administration;
- Hospitalization for 5 days (D-1 morning to D4 morning);
- End of study visit: D4.

For the cohorts 160 mg, 260 mg, 380 mg and 500 mg:

- Screening within 28 days prior to the first administration;

- Hospitalization for 5 days (D-1 morning to D4 morning);
- Ambulatory visits on D5 and D6;
- End of study visit: D6.

Expected duration = approximately 35 days for each subject Expected duration of the trial = 15 months

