3.4.3 End of study

The last visit of the last subject as scheduled in the protocol will be used to determine the end of study (= Day 4 for the cohorts 10 mg, 20 mg, 40 mg and 80 mg or Day 6 for the cohorts 160 mg, 260 mg, 380 mg and 500 mg).

In case an adverse event or an abnormal laboratory result is in follow-up phase after this date, the end of study would be considered as the date of the last examination performed (e.g.: clinical examination or biological analysis) or the last date of contact in case the follow up is longer than expected and the event is assessed as "chronic" or "stable".

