8.3.3. Recording of events

Any AE (including laboratory test/procedures "clinically significant" abnormalities, intercurrent illnesses or injuries, and/or study procedures related AE) reported spontaneously by the subjects, or observed by the Investigator, after IMP administration, will be recorded according to the procedures in force at EUROFINS OPTIMED.

Any untoward medical event, which occurs from the time of signed Informed Consent to the time of IMP administration, will be classified as "pre-dose event" (not considered an adverse event *per se*) and will be recorded according to the procedures in force at EUROFINS OPTIMED.

Any untoward medical event which occurs after the completion of the clinical trial and that is possibly reported by the Investigator to EUROFINS OPTIMED will be classified as a "post-study event" and will be recorded according to the procedures in force at EUROFINS OPTIMED.

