11.2. Sample size

No formal calculation was performed. It has been decided to include 8 subjects (6 active and 2 placebo) within each treatment group, which, given the exploratory nature of the trial, is considered as a sufficient number of subjects.

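### The TEAE table sets no common onset window although observation ends at 72 h for 10–80 mg and at 120 h for 160–500 mg, so a step between 80 and 160 mg can appear without a drug effect

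*Protocol*

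**What the plan says.** Section 3.4.1 gives two schedules. For 10, 20, 40 and 80 mg it states "End of study visit: D4"; for 160, 260, 380 and 500 mg it states "End of study visit: D6". Section 3.4.3 repeats the split: "Day 4 for the cohorts 10 mg, 20 mg, 40 mg and 80 mg or Day 6 for the cohorts 160 mg" and above. The detailed flow chart places D4 at T72h and D6 at T120h.

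Section 11.1.2.1 fixes the TEAE display: "The treatment emergent AEs will be summarised by Primary System Organ Class, Preferred Term and dose group for the safety set". It counts events and subjects reporting them. A TEAE is an event that first appears, or worsens, during exposure to drug; no limit in hours is given. Section 8.3.3 adds a further category: "Any untoward medical event which occurs after the completion of the clinical trial" is classed as a post-study event.

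Section 11.1.2.2 describes vital signs and ECGs at each evaluation and also at the end of the study, with changes from baseline to the end-of-study visit. Section 11.1.2.3 describes laboratory values at named visits and marks D6 as applying to 160 mg and above only.

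**The concern.** Safety by dose is the main purpose of this trial, and the TEAE table by dose group is the display most readers will use to judge it. The upper four doses have a longer period in which an event can occur and more scheduled procedures that can detect one. Under sections 8.1.4 and 8.3.1, a clinically significant abnormality found at such a procedure is recorded as an adverse event. A table without a common window can therefore show more events from 160 mg upwards even if the drug does nothing, and the step would fall exactly where the schedule changes. A real increase would be hard to tell from an artefact of follow-up. A placebo group pooled over all cohorts would not resolve this, because half of its subjects would be observed to 72 h and half to 120 h.

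**Working it through.** **Inputs from the protocol.**
- Eight cohorts of 6 active and 2 placebo subjects: 8 × (6 + 2) = 64, which reproduces the planned total. If all cohorts run, there are 24 active subjects at 10–80 mg and 24 at 160–500 mg.
- Scheduled observation of 72 h and 120 h, a ratio of 120/72 = 1.67.
- A half-life of about 20 h in the first three cohorts (section 3.3.3.2). Five half-lives are 5 × 20 = 100 h, as the protocol states. So 72 h is 3.6 half-lives and 120 h is 6, and drug exposure does not itself impose a shared window.

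**Detection (section 8.2.2).** After dosing, the lower cohorts have laboratory panels on D2 and D4 (two); the upper cohorts have D2, D4 and D6 (three). Hormone tests number one against two. The upper cohorts also have ECGs on D5 and D6 and, on D6, physical and neurological examinations and the questionnaires.

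**Assumption.** The protocol gives neither the background risk of a TEAE by 72 h (p) nor the shape of the hazard. I take p = 10, 20 and 30%, no drug effect, and two hazard shapes.

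*Constant hazard:* risk at 120 h = 1 − (1 − p)^(120/72). For p = 0.20 this is 1 − 0.80^1.667 = 0.311.

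*Hazard falling with a 20 h half-life:* the ratio of cumulative hazards is (1 − 2^(−6))/(1 − 2^(−3.6)) = 0.9844/0.9175 = 1.073. For p = 0.20 the risk at 120 h is 1 − 0.80^1.073 = 0.213.

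| Assumed risk by 72 h | Risk by 120 h, constant hazard | Expected subjects, lower v upper 24 | Risk by 120 h, falling hazard | Expected subjects, lower v upper 24 |
|---|---|---|---|---|
| 10% | 16.1% | 2.4 v 3.9 | 10.7% | 2.4 v 2.6 |
| 20% | 31.1% | 4.8 v 7.5 | 21.3% | 4.8 v 5.1 |
| 30% | 44.8% | 7.2 v 10.8 | 31.8% | 7.2 v 7.6 |

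**How often the table would mislead.** Under constant hazard, exact binomial calculation gives the chance that the upper half of the dose range shows more subjects with a TEAE than the lower half. For p = 10/20/30% it is 66.1/76.5/82.2%, and it spans 56–88% for p between 5 and 50%. With equal windows it would be 36–44% over the same range, the rest being ties or the reverse order. Under the falling hazard the excess is 0.2 to 0.5 subjects of 24 for p between 10 and 40%.

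**Which displays are affected.** The TEAE table has no window. The end-of-study summaries in 11.1.2.2 put D4 values for the lower doses beside D6 values for the upper doses. The laboratory tables, and the vital-sign and ECG summaries at each evaluation, already set D4 against D4.

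**The case against.** The strongest reply is that the effect may be small and is visible to a careful reader. Day 1 is densely assessed, while D5 and D6 are single outpatient visits, and if events follow plasma levels the excess is a fraction of a subject. Even under constant hazard at 20%, one dose group of six goes from 6 × 0.20 = 1.2 to 6 × 0.311 = 1.9 expected subjects. Adverse events are listed with onset time and delay since dosing, so late events can be identified. The safety analysis is descriptive, so no formal safety test is biased. Escalation rests on blinded review of each cohort, not on the final tables. The longer follow-up also has a stated reason, the observed half-life.

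Most of this stands as mitigation, and the longer schedule is not in question. But a listing does not correct a summary table, and background or procedure-detected events need not follow plasma levels.

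Two stronger readings are tempting. The first is that every primary safety table is affected. It is not supported: the by-visit displays compare like with like. The second is that the primary safety analysis has no placebo comparator, although the objective in section 2.1 reads "in healthy male subjects, compared to matching placebo". A reader might infer this because sections 11.1.2.1 to 11.1.2.3 do not mention placebo and section 11.2 speaks of "8 subjects (6 active and 2 placebo) within each treatment group". But those sections neither exclude placebo nor say it is merged with active, and the section 11.2 sentence concerns sample size and defines no analysis column. Placebo layout is ordinary content for a statistical analysis plan, which is not at hand.

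**Conclusion.** The point holds for the TEAE table and the end-of-study vital-sign and ECG summaries. As written, observation time and detection are confounded with dose at the 80/160 mg boundary, so an apparent step can arise there without a drug effect. That such a step will appear is more than the documents support. The size runs from material (20% becoming 31% under constant hazard) to small (20% becoming 21.3% if the hazard falls with the half-life), and both figures rest on an assumed background rate. The additional D5–D6 procedures are not in this arithmetic and could add to the difference. How many events are lost after D4 in the lower cohorts also depends on whether completion of the trial in section 8.3.3 means the subject's last visit or the end of the whole trial; the text allows either. Following ongoing events beyond the last visit does not replace looking for new ones.

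**What to change.** In section 11.1.2.1, or in the statistical analysis plan before unblinding:
- Make TEAEs with onset 0–72 h after dosing the main table for all groups, placebo included.
- Show TEAEs with onset after 72 h in a separate table for 160–500 mg, against the placebo subjects of those same cohorts.
- In section 11.1.2.2, label end-of-study values by day and use D4 as the common time point, with D6 shown separately.

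The by-visit laboratory, vital-sign and ECG tables stay as they are. No new data or visits are needed, since onset times are already collected. The cost is one extra table, and the main table omits late-onset events, which the second table shows. Column sizes should follow the cohorts actually run, since section 1.4 says some may not be performed.

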11.1.2.2. Physical examination, neurological examination, ECG, vital signs and questionnaires

Physical examination, neurological examinations, ECGs, vital signs and questionnaires (C-SSRS, Bond and Lader VAS) recorded during the study will be individually listed and quantitative parameters will be summarised by using descriptive statistics.

For vital signs and ECG parameters, values and abnormalities (not clinically significant and clinically significant) will be described by dose group and overall, at screening, study baseline (D-1 or D1 pre-dose), each evaluation under treatment phase and at the end of the study.

Change between the value at baseline and the value at each evaluation under treatment phase and at end of study visit will be described for each parameter by dose group and overall.

11.1.2.3. Laboratory parameters

All laboratory values recorded during the study will be individually listed and flagged for values outside reference ranges and for clinical significance (assessed by investigator). Quantitative and qualitative parameters will be summarised by descriptive statistics.

Values, position according to laboratory range and clinical assessment will be described at screening, D-1 (baseline), at D2, D4 and D6 (only for the cohorts 160 mg, 260 mg, 380 mg and 500 mg) by dose group and overall.

Change between the value at baseline and the value at post-dose visits will be described for each parameter by dose group and overall.

11.1.3. Analysis of secondary criteria

Pharmacokinetic

A detailed SAP will be prepared by PhinC Development. This SAP should be validated by the Sponsor prior to unblinding.

The summary tables and data listings will be produced by PhinC Development.

Concentrations will be presented by dose level and time point. Descriptive statistics for the concentrations will be presented as mean, SD, and will be calculated if at least 2/3 of the values per time-point are above LOQ. For descriptive statistics calculations, plasma concentrations below the limit of quantification will be set to zero (0) before the first concentration equal or above LOQ and considered as missing after.

No descriptive statistics will be done on urine concentrations.

Individual PK parameters will be presented by dose level. Descriptive statistics of the PK parameters will be presented as mean, SD, coefficient of variation (CV%), median, geometric mean (GM), Min, and Max and will be calculated if at least 2/3 of the reliable PK parameters are available.

A measured plasma drug concentration vs. actual time curve will be produced in graphic for each subject on both linear/linear and log/linear scales. Mean plasma drug concentration vs. time curves will also be produced for each dose level, separately.

The individual AUC and Cmax values will be presented graphically by dose level.

Dose proportionality

The hypothesis that AUC and C_{max} are dose proportional will be formally tested using a power model approach. AUC and C_{max} values, for all dose levels, will be analyzed for dose proportionality using analysis of variance (ANOVA) techniques.

Data will be fitted to the following model:

$$log(AUC or C_{max}) = \mu + [\beta \times log(Dose)]$$

This is usually referred to as a power model because after exponentiation:

AUC or
$$C_{max} = \alpha \times Dose^{\beta}$$

Prior to the analysis, the assumption of a linear relationship between the log AUC (C_{max}) and log-dose will be tested using ANOVA by partitioning the sums of squares for treatments into those for linearity and departures from linearity. If the departures from linearity are significant then the hypothesis of dose proportionality is rejected and the power model analysis will not be performed.

In case, $AUC_{0-\infty}$ could not be considered as reliable in a majority of subjects (e.g. too large percentage of extrapolation, poor quality of k_e determination), dose proportionality assessment will be performed on AUC_{0-t} values.

The estimate obtained for β is a measure of dose proportionality. The estimate of β together with its 90% CI (β_{l} , β_{u}) will be presented to quantify the degree of non-proportionality.

The dose proportionality will be confirmed if the 90% CI of β (β_I , β_u) is contained completely within the following critical region:

$$\left[\Theta_{L};\Theta_{H}\right] = \left[1 + \frac{\log(0.8)}{\log(r)};1 + \frac{\log(1.25)}{\log(r)}\right]$$

where r, defined as the dose ratio, is equal to h/I, h being the highest dose and I the lowest dose.

In this decision rule, the dose proportionality will be analyzed as an equivalence problem. If the 90% CI is excluded completely from the critical region $\left[\Theta_L;\Theta_H\right]$ defined here above, the hypothesis of dose proportionality is rejected. If the 90% CI of β includes the lower or the upper bound of the critical region, no conclusion can be done on dose proportionality. The proportionality will be tested at a 5% significance level.

The calculation of the increase in AUC and C_{max} for a two-fold increase in dose will be performed by substituting the value of β in the equation 2^{β} . CI for this ratio will be obtained by substituting β_{l} and β_{u} in the equation 2^{β} .

Assessment of the dose proportionality will be performed on the complete dose range. In case of departures from linearity or of negative conclusion of dose proportionality on the complete dose range, further investigation using the same methodology might be done on a restrained dose range.

The statistical package SAS[®] v.9.4 will be used to perform all statistical analyses.

Pharmacodynamic

In case the Holter data are analysed, the following analyses will be reported in a separate report:

All ECG parameters for PD analysis will be extracted in triplicate from 24-hours Holter recording. Extraction will be matched to PK sampling time and triplicate values will be averaged in order to obtain one single value per time point. Individual data listings and descriptive statistics by dose level and time point will be performed.

All parameters will be presented descriptively and graphically on raw data and changes from baseline by dose level and time points.

Categorical analysis consisting in counts and percentages of abnormal values per dose level will be performed for HR, QTc, PR and QRS according to regulatory thresholds for raw data and changes from baseline.

Treatment emergent morphological findings will be summarized as counts and percentage of subjects presenting at least one finding by dose level.

Concentration-response relationship will be investigated between change from baseline in QTcF and DNDI-6148 concentrations. First, graphics of change from baseline in QTcF and concentrations of DNDI-6148 will be generated in order to visualize the overall pattern of each relationship. Modelling of each of these graphics will then be performed by means of linear or nonlinear mixed model.

For each compound, a model will be selected according to the overall precision of the model towards observed data and diagnostic plots. Using these models, predictions of changes from baseline at concentrations of interest (e.g. Cmax) will be obtained from the concentration-response models with their 90%CI.

